3.5 Study Endpoints

The primary outcomes of this study are:

- 1) **Abundance of microbes that produce SCFA** (e.g., *Bifidobacteria*, *Eubacterium*, and *Clostridium*^{56,57}) will be evaluated by whole genome sequencing (WGS). WGS will be performed in fecal samples before and after the 12 week intervention to obtain a holistic representation of the microbes in the gut and to confirm that the blueberry powder interacts with the gut microbiota WGS was chosen because it enables identification of microbes down to the specific species or strain of bacteria whereas other methods can only identify the genus level. Also, WGS tends to be less biased compared to 16S rRNA sequencing. A reputable lab (e.g., Microbial Omics Core at the Broad Institute) will perform the DNA extraction from fecal samples and whole genome sequence library construction and sequencing. Then the Fastq sequences will be processed and analyzed by a reputable lab (e.g., the Harvard Chan Microbiome Analysis Core).
- 2) **Fecal SCFA** will be measured by a reputable lab (e.g., West Coast Metabolomics Center at University of California Davis). Following sample preparation outlined in §5.2, a biphasic extraction will be performed to extract the SCFA from the fecal samples. SCFA will be separated and identified using gas chromatography mass spectrometry. Internal standards and an external curve will be used to calculate the concentration of SCFA in each sample (acetate, propionate, and butyrate).
- 3) **Depressive symptom severity** will be assessed by the original CES-D⁵⁸ and the CESD-R,⁵⁹ which are validated questionnaires of questions regarding feelings of depression, worthlessness, loneliness, energy level, and fear. See §5.2 for more information.

3.6 Study Intervention Products

In the parent study, participants will be randomized to consume either 48 g of freeze-dried blueberry powder (**equivalent to ~2 cups of fresh, whole blueberries**) or 48 g of placebo powder each day for this 12 week intervention. A single batch of freeze-dried blueberry powder and a single batch of placebo powder will be provided by the US Blueberry Council. A 48 g dose of the freeze-dried blueberry powder provides ~8 g of dietary fiber and ~600 mg of anthocyanins. The powder will be packaged into individualized packets (24 g/packet), and individuals will be instructed to consume 1 packet in the morning and 1 in the afternoon (i.e., 48 g/day). The placebo powder is a nutritionally matched powder (primarily consisting of maltodextrin, fructose, and dextrose) that is devoid of dietary fiber and anthocyanins. *Given that microbes are ubiquitous (even on blueberries⁶⁰), we will evaluate the microbial content of the freeze-dried blueberry and placebo powder. We will preliminarily explore if microbes on foods are similar to the microbes that reside and proliferate in the gut.* Prior to the intervention, similar methods will be used as described for the fecal microbiota techniques in §3.5

To allow for blinding, the placebo powder will be labeled with either a letter or number that is different from the intervention powder. This is a double-blind intervention, so neither the participants nor the study staff will know which powder is the placebo and/or which is the blueberry powder. See §3.6 for further information on dietary intervention.

CHAPTER 4 RECRUITMENT AND DATA COLLECTION

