3.4 Number of Subjects and Study Duration

The parents study aims to recruit a total of 40 individuals (both men and women), in proportion to the gender and racial distribution of the greater Boston population, through local newspaper and internet advertisements, physician referrals, our registry of research volunteers, Hebrew SeniorLife (HSL) senior housing sites, and patient registries (e.g., HRC or Beth Israel Deaconess Medical Center). Participants will remain in the study for a total of 14 weeks.

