4.5 Minimization of Bias

This study is designed as a double-blind intervention so neither staff nor participants are aware of their assigned intervention arm.

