5.3 Dietary Intervention

The duration of this study will be a total of 14 weeks. The first two weeks will require participants to avoid eating fiber- and anthocyanin-rich foods.

Individuals will then be randomized to either the intervention or the control group. This is a double-blinded study, so the study staff not the participant will know what powder the participants are assigned to. Those randomized to the intervention group will be asked to consume approximately 48 g of freeze-dried blueberry powder as a source of ~8 g of fiber and 600 mg of anthocyanins. The proposed dose of 48 g of freeze-dried blueberry powder is equivalent to approximately 2 cups of whole blueberries. Individuals randomized to the control group will be asked to consume approximately 48 g of a nutritionally matched placebo powder that is devoid of anthocyanins and fiber.

The powders will be individually packaged in 24 g amounts. Participants will be instructed to consume their respective powder, mixed in an 8 fl oz glass of water twice per day for 12 weeks. They will be asked to consume 24 g in the morning and 24 g in the afternoon. Given that intervention and control products are regularly consumed, we do not anticipate any toxicities.

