6.2 Aim Statistical Methods and Power

Aim 1 Hypothesis: The abundance of microbes that produce SCFA increase after 12 weeks of dietary fiber and anthocyanin supplementation compared to placebo. **Aim 1 Analysis:** To determine taxa and pathways that differ significantly by treatment (blueberry vs. placebo powder), multivariate analyses that accounts for covariates will be carried out using MaAsLin2⁶³ (Multivariate Analysis by Linear Models). MaAsLin2 performs a mixed-effects linear regression of individual log-transformed microbial features (response) on categorical or continuous factors (explanatory variables). A random effects model will be used for repeated measures (i.e., longitudinal data). Linear models will be constructed to assess each feature independently, and adjusted for false discovery using Benjamini-Hochberg FDR. The output of MaAsLin will reveal whether cohort participants with different dietary exposures also differ in relative abundance of a particular bacterial species or pathway in the gut. **Aim 1 Expected Results/Power:** With our proposed sample size of 20/group, we anticipate power 0.95 to detect a 0.314-unit difference in common taxa (~14310 sequences and 0.0954 relative abundance at 5% read usage rate), and a 0.122-unit difference in rare taxa (~2222 sequences and 0.0148 relative abundance at 5% read usage rate) collected at the 2 time points. Approximating as above, the corresponding detection limit for 250 pathways is power 0.95 for a 0.0013-unit difference (1282 sequences at a 33% read usage rate). We assumed we will observe 250 pathways.

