Risk Minimization of Intervention Product: Individuals with allergies to intervention products will not be included in this study to avoid any adverse effects/allergic reactions. We anticipate that the blueberry and placebo powder will be well-tolerated by participants since they consist of dietary nutrients that are regularly consumed. Regardless, every 4 weeks we will ask participants about any complaints or adverse events that are directly related to the study intervention products. We plan to track diarrhea, gas, bloating, abdominal pain, constipation etc. Since the intervention arm will be increasing fiber consumption and sudden changes in fiber intake may cause gastrointestinal distress, participants will be counseled to consume their dietary intervention products alone (i.e. without other foods) to avoid consumption of large quantities of fiber at one time. Since our intervention provides only ~30% of the recommended intake of daily fiber, we do not anticipate this amount will result gastrointestinal distress, if consumed alone. Nevertheless, symptoms of gastrointestinal distress will be captured at each visit and appropriately addressed by the study team. [name], who has a PhD in Nutrition, will consult with participants on their experience with the fiber and reconcile any gastrointestinal stress. If a participant develops a health problem or a potential health problem (in addition to the ones outlined below), the PI will be notified ASAP. If necessary, the SO will be contacted to help decide whether the participant should continue in the study, and/or what further steps regarding medical evaluation should be performed.

Risk Minimization of Depression Severity: Although we do not anticipate a change to a more severe form of depression, we recognize that our proposed population of older adults with prevalent

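### Section 3.6 reads as one label code per arm, so learning one code reveals all 40 allocations to anyone who sees the labels

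*Combined protocol and SAP*

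**What the plan says.** Section 3.6 describes the supply and the blind together. On supply: "A single batch of freeze-dried blueberry powder and a single batch of placebo powder will be provided by the US Blueberry Council". On labelling: "the placebo powder will be labeled with either a letter or number that is different from the intervention powder". On the aim of the label: "neither the participants nor the study staff will know which powder is the placebo and/or which is the blueberry powder". Section 4.5, the whole of the text on minimizing bias, adds only that "neither staff nor participants are aware of their assigned intervention arm".

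No section describes participant-specific packet numbers, more than one code per arm, a holder of the code key, a procedure for breaking the code for one participant, or a check on whether the blind held. Sections 3.6 and 5.3 mention individual packets of 24 g, but that describes portion size. The unique study number in sections 4.4, 7.1 and 8.2 identifies data, not powder.

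On what happens at visits, section 5.2 has participants return used and unused packets. Sections 5.1 and 5.2 place compliance, symptoms and depressive symptoms together at weeks 4, 8 and 12. Section 8.2 says of symptoms: "We plan to track diarrhea, gas, bloating, abdominal pain, constipation etc". Section 5.4 makes depressive symptom severity the primary endpoint.

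**The concern.** When a whole arm shares one code, the blind has a single secret. Each participant's experience is a clue to what the shared code means, so clues that are weak one at a time add up over as many as 20 people. Once the meaning of one code is known or guessed, the other follows by elimination.

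The protocol supplies both the occasion and a possible clue. Returned packets, symptom reports and the CES-D meet at the same visits. Section 8.2 notes that the intervention arm raises its fiber intake, and that sudden changes in fiber may cause gastrointestinal distress. It also has a team member talk with participants about their experience with the fiber.

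At stake is the CES-D, a questionnaire about feelings. Section 8.2 has trained research staff administer the questionnaires on sensitive topics. Staff who believe they know the arm may affect how answers are elicited at the remaining visits. The effect that section 6.2 sets out to detect is 2 points on the CES-D, and section 8.6 says that later trials will be designed from the variation in change seen here.

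**Working it through.** The plan states no figure on this point, so there is none to reproduce. The check has two parts: the reading of the text, and a count.

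**Reading.** Three features of section 3.6 point to one code per arm: the label is a letter or a number, in the singular; it is attached to one of two powders, each from one batch; and the blind is defined as not knowing which powder is which, not which packet holds what. Section 5.3 confirms two groups: "Individuals will then be randomized to either the intervention or the control group". Nothing elsewhere adds a code at participant level.

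**Count.** Inputs:
- total sample size N = 40 (section 3.4);
- participants per arm n = 20 (section 6.2: "With our proposed sample size of 20/group");
- codes per arm k, with k = 1 as section 3.6 reads. Larger k are illustrations, not figures from the protocol.

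Let R be the number of allocations revealed to a person who sees all the labels and learns the meaning of one code.
- For k = 1, the 20 holders of that code are revealed, and the 20 holders of the other by elimination: R = 20 + 20 = 40.
- For k > 1, if it is not known which codes belong together, only the holders of that code are revealed: R = n / k.

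| Codes per arm (k) | Calculation | Revealed |
|---|---|---|
| 1 (as section 3.6 reads) | 20 + 20 | 40 of 40 |
| 2 | 20 / 2 | 10 of 40 |
| 4 | 20 / 4 | 5 of 40 |
| 20 (a unique number each) | 20 / 20 | 1 of 40 |

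**Who is exposed.** A participant sees only their own label, so one shared code tells them no more than a unique number would, unless participants compare labels. The pooling route runs through anyone who sees many labels. Staff who handle returned packets would be such people.

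**Which outcomes are exposed.** The CES-D and CESD-R are open to expectation. Microbial abundance and fecal SCFA are measured in laboratories (section 3.5) and are less exposed. Section 3.5 lists all three outcomes as primary, whereas section 5.4 makes only depressive severity primary.

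**The case against.** The strongest reply is that the labels matter only if several further things are true, and that the documents do not establish them. Four stronger readings are tempting and should not be made.

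- *The same staff hand out packets, collect them, record symptoms and administer the CES-D.* A reader might infer this because the tasks fall at the same visits. No section says who dispenses the powder or that one person does all four tasks.
- *The protocol expects gastrointestinal symptoms in the blueberry arm alone.* Section 8.2 says only that they may occur, does not anticipate them at this amount if the product is consumed alone, and tracks symptoms without restriction to one arm.
- *One spilled packet would break the blind.* That holds only if the powders differ visibly. Section 3.6 describes nutritional matching and does not mention appearance. If they do differ, each packet gives itself away, and a unique number would not repair that.
- *One emergency unblinding would break it.* No such procedure is described. Section 8.5 deals with serious events by review or discontinuation.

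It is also fair to say that section 4.5 is not the only protection. Chapter 9 provides standard instructions for each assessment, staff training and checks every six months. These limit how far a staff member's belief can alter the answers, but they do not keep the code from being inferred.

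Finally, randomization belongs to the parent study, whose protocol may specify finer coding, as may the manual of procedures. Section 3.6 does not refer to either for labelling, and it states a method of its own. The possibility is a reason to accept a one-sentence clarification, not to leave the text as it stands.

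**Conclusion.** The point holds as a weakness in the stated labelling method. On the natural reading of section 3.6, knowledge of one code reveals 40 of 40 allocations to a person who sees the labels, against 5 of 40 with four codes per arm and 1 of 40 with unique numbers.

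This rests on three assumptions: that the singular wording means one code per arm; that the person sees every label; and, for the alternatives, that nobody knows which codes belong to the same arm. The 40 is an upper limit on allocations revealed. It is not an estimate of bias. CES-D scores collected before a code is learned are unaffected, and the effect on later ones cannot be computed from the documents.

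A reader might infer that the blind will fail or that the CES-D result will be biased. The documents do not support that: they show a route by which staff blinding could weaken, not evidence that it would. The change is worth making before packing because it is cheap and protects the endpoint most open to expectation.

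**What to change.** In section 3.6, replace the single letter or number with participant-specific packet numbers generated from the randomization list, or at least several codes per arm. State that the key is held by an existing team member who has no contact with participants. If the parent study already does this, one sentence saying so is enough.

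The same edit should reconcile a sentence in section 5.3 which, read literally, says that study staff will know the assigned powder. It is probably a slip of one letter, but as printed it contradicts sections 3.6 and 4.5.

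The cost is a small amount of labelling and kit-list work before packing, shared with the parent study. The powder already goes into individual packets, and neither the sample size, the visits nor the analysis changes.

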4.1 Recruitment Overview

Participants will be recruited from the Boston area community, including senior housing facilities in urban/suburban areas and research recruitment repositories. We will utilize a multi-pronged approach to meet our recruitment goals:

- We will recruit from the research repository that resides at HRC
- We will connect with social workers in and outside the HRC
- We will perform medical record reviews to identify potentially eligible individuals at the Hebrew SeniorLife (HSL) geriatric medicine practices.
- We will advertise through direct mailings to all residents of HRC's seven supportive housing facilities (over 3,000 residents).
- We will give presentations at each Hebrew SeniorLife (HSL) facility.
- We will use the Harvard Catalyst (CTSA) Shared Health Research Information Network (SHRINE) to identify volunteers from Harvard-affiliated hospitals and clinics.
- We will advertise our study within numerous local media outlets, on HRC's Hinda and Arthur Marcus Institute for Aging Research and other websites (e.g., Craig's List), and at www.clinicaltrials.gov.

4.2 Informed Consent

All interested individuals will be asked to provide verbal consent to complete an initial eligibility screen during a phone conversation with study personnel. Potentially eligible participants will then schedule an in-person screening visit. Potential participants may be sent by email or conventional post (per request, and according to their preference) a copy of the informed consent form for them to review at their own pace prior to the in-person screening. Written informed consent will be obtained by study personnel at the beginning of the in-person screening visit.

4.3 Participant Withdrawal

Any participant who expresses a desire to discontinue participation in the study will be withdrawn at their request immediately. All data collected prior to withdrawal will be maintained in the study data set.

Additionally, a subject may be withdrawn from the study prior to completing all of the study related procedures due to the following conditions:

- Subject safety issues
- Failure of subject to adhere to protocol requirements
- Disease progression
- Subject decision to withdraw from the study (withdrawal of consent)

Withdrawn subjects may not reenter the study unless there are extenuating circumstances (e.g. family emergency or required travel out of town) that interfere with the start of the study before any medications are administered. In this case, they may be scheduled to start over again. If new medical conditions arise or are exacerbated during the study intervention, the withdrawal of a participant will be evaluated by the PI, SO, and/or study psychiatrist.

4.4 Methods to Protect Participant Privacy

The following are the planned procedures for effectively protecting against and minimizing loss of participant privacy:

1. Phone screening will be conducted in a private office space.
2. Study visits will be conducted in private rooms.
3. Each participant will be given a unique study identification number and data will not include any of the participant's PHI.
4. All participant-identifying information will be stored and managed on a secured database server. The information will be password protected.
5. Participant confidentiality will be maintained in accordance with Health Insurance Portability and Accountability Act (HIPAA) regulations.
6. Only the PI, study personnel, and laboratory personnel approved by the IRB and authorized to view PHI will have access to the information.

7. PHI will not be used during discussion, presentation or publication of any research data.
8. Files containing PHI data collected for recruitment and screening purposes will be kept in locked, secured filing cabinets accessible only to designated study personnel (research assistants and investigators)

4.5 Minimization of Bias

This study is designed as a double-blind intervention so neither staff nor participants are aware of their assigned intervention arm.

4.6 Maximizing Compliance and Minimizing Attrition

At the start of an individual's study participation, he/she will be given a schedule of their study visits. Visits will be scheduled at a time of day that the participant determines is most convenient for them, and will be repeated at the same time for each visit. Transportation will be provided for each visit as needed, snacks will be available, and stipends will be provided for each study milestone. If necessary, reminder calls will be made to participants on approximately 2 days prior to study visits.

Participants will be tracked throughout their enrollment. Each study visit will be documented. Some study visits will be followed with a brief telephone check-in to ask the participant questions about medication compliance, adverse effects, and their experience during the most recent visit. All calls to the participant and their feedback will be carefully tracked. Notes that may facilitate compliance, such as "call before 10 am," etc., will be kept in participant files.

We will employ specific strategies to maximize participation and compliance:

- **Positive Framing about Benefits:** Information will be presented in terms of the possible gains rather than the avoidance of losses as this is a more effective motivational approach.
- **Feedback and Recognition of Progress:** Participants will be acknowledged throughout their participation with thank you notes, and will be recognized for their contributions to the study through regular brief flyers/newsletters such as "Partners in Progress – Mobility and Falls updates". We will remain in close contact with individuals throughout their participation with follow-up calls each month.
- **Incentives and Rewards:** Participants will receive snacks at each visit, cards for achieving milestones, such as birthdays, holidays, etc.; and certificates of completion.

CHAPTER 5. RESEARCH METHODS

5.1 Participant Visit Schedule

All study visits will take place at the Clinical Research Laboratory at HRC, Roslindale, MA, an HRC-affiliated housing site, or at the participants home (if possible).

Participant eligibility will be determined during an in-person screening that is a part of the parent study. If eligible and interested, the participant will be asked to continue with 5 additional visits. The assessments/activities for the study visits pertaining to this specific ancillary study are outlined below. Some measures (e.g., safety measures) will overlap with the parent study and are indicated with a *.

The majority of subjects that will enroll in this ancillary study will undergo screening as a part of the parent study as outlined in **IRB Pro00064749**. However, if a participant wants to enroll only in this ancillary study, the participant will need to undergo the telephone screening and in-person screening visits as outlined in the parent study (**IRB Pro00064749**).

Visits

Assessments and Medication Administration at Each Visit

Baseline Visit, Week 0:	Assessments/Activities: 1. Turn in Diet Records* 2. Provide Fecal Sample 3. Depressive Symptoms 4. Positive/Negative Affect 5. Suicidal Ideation* 6. Symptoms*
Week 4 Visit:	Assessments/Activities 1. Turn in Diet Records* 2. Depressive Symptoms 3. Positive/Negative Affect 4. Suicidal Ideation* 5. Symptoms* 6. Compliance*
Week 8 Visit:	Assessments/Activities 1. Turn in Diet Records* 2. Depressive Symptoms 3. Positive/Negative Affect 4. Suicidal Ideation* 5. Symptoms* 6. Compliance*
Week 12 Visit:	Assessments/Activities: 1. Turn in Diet Records* 2. Provide Fecal Sample 3. Depressive Symptoms 4. Positive/Negative Affect 5. Suicidal Ideation* 6. Symptoms* 7. Compliance*

